## **7.2. Laboratory Evaluations**

Summaries of laboratory data will be provided for the safety analysis set and will include data collected up to last dose of any study drug plus 30 days (except HIV RNA and CD4 data, which is through the end of the study) for subjects who have stopped all study drugs and all available data at the time of the database snapshot for subjects who are ongoing at the time of this analysis. Analysis will be based on values reported in conventional units. Laboratory results cancelled by the central laboratory will not be included in analysis.

No inferential statistics will be generated.

### **7.2.1. Summaries of Numeric Laboratory Results**

Descriptive statistics (sample size, mean, standard deviation, median, Q1, Q3, minimum and maximum) will be provided by treatment group for ALT, AST, total bilirubin, alkaline phosphatase, white blood cell (WBC) counts, neutrophils, lymphocytes, hemoglobin, platelets, reticulocytes, PT, and INR, and CD4 counts (absolute and %) as follows:

- Baseline values
- Values at each post-baseline analysis window
- Change from baseline at each post-baseline analysis window

The mean, median, Q1, Q3, minimum and maximum will be displayed to reported number of digits, standard deviation to reported number of digits +1 for visits up to end of treatment.

Median (Q1, Q3) of the absolute values for these laboratory parameters will be plotted by treatment group and visit. In the case of multiple values in an analysis window, data will be selected for analysis as described in Section 3.6.3.

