**Table 1-1. GS-US-334-0131: Cohort 1 Preliminary Pharmacokinetic Analysis**

Cohort 1: Sixteen subjects completed the study procedures and the data are as follows:

Effect of ATR (EFV/FTC /TDF) on GS-7977 (n=16)			
GS-7977			
Mean (%CV)	GS-7977 alone	GS-7977 + ATR	%GMR (90%CI)
AUC inf (ng.hr/ml)	827 (41.7)	777 (41.1)	93.9 (75.9-116)
C max (ng/ml)	1020 (47.7)	877 (64.0)	80.9 (59.6-110)
GS-566500			
Mean (%CV)	GS-7977 alone	GS-7977 + ATR	%GMR (90%CI)
AUC inf (ng.hr/ml)	1140 (27.8)	895 (28.2)	79.2 (69.4-90.4)
C max (ng/ml)	308 (37.5)	218 (37.2)	72.1 (62.2-83.7)
GS-331007			
Mean (%CV)	GS-7977 alone	GS-7977 + ATR	%GMR (90%CI)
AUC inf (ng.hr/ml)	11,300 (19.0)	9,620 (25.7)	84.0 (76.2-92.5)
C max (ng/ml)	1,250 (24.2)	965 (26.8)	76.7 (69.8-84.3)
Effect of GS-7977 on ATR (EFV/FTC/TDF) (n=16)			
TDF			
Mean (%CV)	ATR alone	ATR + GS-7977	%GMR (90%CI)
AUC tau (ng.hr/ml)	2,270 (22.6)	2,210 (20.3)	97.7 (91.1-105)
C max (ng/ml)	274 (32.0)	343 (29.6)	125 (108-145)
C trough (ng/ml)	43.7 (23.1)	42.9 (20.6)	98.6 (91.3-106)
FTC			
Mean (%CV)	ATR alone	ATR + GS-7977	%GMR (90%CI)
AUC tau (ng.hr/ml)	9,910 (17.6)	9,810 (17.2)	99.1 (93.7-105)
C max (ng/ml)	1,840 (28.6)	1,780 (27.2)	96.9 (87.6-107)
C trough (ng/ml)	69.2 (22.0)	73.0 (25.6)	104 (97.6-111)
EFV			
Mean (%CV)	ATR alone	ATR + GS-7977	%GMR (90%CI)
AUC tau (ng.hr/ml)	70,900 (56.2)	69,600 (62.7)	96.7 (90.8-103)
C max (ng/ml)	4,410 (45.2)	4,250 (50.7)	94.7 (84.6-106)
C trough (ng/ml)	2,310 (68.0)	2,280 (75.4)	96.9 (94.0-99.8)

Modest decreases in systemic exposure of GS-7977 and GS-566500 (GS-56500 Cmax decreased by 28%) with no effect on GS-331007 were noted on co-administration of GS-7977 with ATR. TDF, FTC and EFV PK were unaltered by GS-7977, with the exception

of a slight increase in TDF Cmax (25%) that is not considered to be clinically significant. Based on these results, GS-7977 can be co-administered with ATR or its components (TDF, FTC, FTC/TDF and EFV).

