Infant, ≤ 14 Days (hemolytic)	NA	NA	20.0 to 25.0 mg/dL 342 to 428 µmol/L	> 25.0 mg/dL > 428 µmol/L
Blood Urea Nitrogen	1.25 to 2.50 × ULN	> 2.50 to 5.00 × ULN	> 5.00 to 10.00 × ULN	> 10.00 × ULN
Hyperuricemia	>ULN to 10.0 mg/dL >ULN to 597 µmol/L	> 10.0 to 12.0 mg/dL > 597 to 716 µmol/L	> 12.0 to 15.0 mg/dL > 716 to 895 µmol/L	> 15.0 mg/dL > 895 µmol/L
Hypouricemia	1.5 mg/dL to < LLN 87 µmol/L to < LLN	1.0 to < 1.5 mg/dL 57 to < 87 µmol/L	0.5 to < 1.0 mg/dL 27 to < 57 µmol/L	< 0.5 mg/dL < 27 µmol/L
Creatinine	> 1.50 to 2.00 mg/dL > 133 to 177 µmol/L	> 2.00 to 3.00 mg/dL > 177 to 265 µmol/L	> 3.00 to 6.00 mg/dL > 265 to 530 µmol/L	> 6.00 mg/dL > 530 µmol/L
Bicarbonate	16.0 mEq/L to < LLN 16.0 mmol/L to < LLN	11.0 to < 16.0 mEq/L 11.0 to < 16.0 mmol/L	8.0 to < 11.0 mEq/L 8.0 to < 11.0 mmol/L	< 8.0 mEq/L < 8.0 mmol/L
Triglycerides (Fasting)	NA	500 to 750 mg/dL 5.64–8.47 mmol/L	> 750 to 1200 mg/dL > 8.47–13.55 mmol/L	> 1200 mg/dL > 13.55 mmol/L
LDL (Fasting)	130 to 160 mg/dL 3.35 to 4.15 mmol/L	>160 to 190 mg/dL >4.15 to 4.92 mmol/L	> 190 mg/dL >4.92 mmol/L	NA
Pediatric >2 to <18 years	110 to 130 mg/dL 2.84 to 3.37 mmol/L	>130 to 190 mg/dL >3.37 to 4.92 mmol/L	> 190 mg/dL >4.92 mmol/L	NA

CHEMISTRY				
	Grade 1	Grade 2	Grade 3	Grade 4
Hypercholesterolemia (Fasting)	200 to 239 mg/dL 5.16 to 6.19 mmol/L	> 239 to 300 mg/dL > 6.19 to 7.77 mmol/L	> 300 mg/dL > 7.77 mmol/L	NA
Pediatric < 18 Years	170 to 199 mg/dL 4.39 to 5.15 mmol/L	> 199 to 300 mg/dL > 5.15 to 7.77 mmol/L	> 300 mg/dL > 7.77 mmol/L	NA
Creatine Kinase	3.0 to < 6.0 × ULN	6.0 to < 10.0 × ULN	10.0 to < 20.0 × ULN	≥ 20.0 × ULN

\*Calcium should be corrected for albumin if albumin is < 4.0 g/dL

ENZYMES				
	Grade 1	Grade 2	Grade 3	Grade 4
AST (SGOT)	1.25 to 2.50 × ULN	> 2.50 to 5.00 × ULN	> 5.00 to 10.00 × ULN	> 10.00 × ULN
ALT (SGPT)	1.25 to 2.50 × ULN	> 2.50 to 5.00 × ULN	> 5.00 to 10.00 × ULN	> 10.00 × ULN
GGT	1.25 to 2.50 × ULN	> 2.50 to 5.00 × ULN	> 5.00 to 10.00 × ULN	> 10.00 × ULN
Alkaline Phosphatase	1.25 to 2.50 × ULN	> 2.50 to 5.00 × ULN	> 5.00 to 10.00 × ULN	> 10.00 × ULN
Total Amylase	> 1.0 to 1.5 × ULN	> 1.5 to 2.0 × ULN	> 2.0 to 5.0 × ULN	> 5.0 × ULN
Pancreatic Amylase	> 1.0 to 1.5 × ULN	> 1.5 to 2.0 × ULN	> 2.0 to 5.0 × ULN	> 5.0 × ULN
Lipase	> 1.0 to 1.5 × ULN	> 1.5 to 3.0 × ULN	> 3.0 to 5.0 × ULN	> 5.0 × ULN
Albumin	3.0 g/dL to < LLN 30 g/L to < LLN	2.0 to < 3.0 g/dL 20 to < 30 g/L	< 2.0 g/dL < 20 g/L	NA

URINALYSIS				

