#### 7.2.2.1. Treatment-Emergent Laboratory Abnormalities

Treatment-emergent laboratory abnormalities are defined as values that increase at least 1 toxicity grade from baseline at any time post-baseline up to the last dose of any study drug plus 30 days (except CD4 which is through the end of the study) for subjects who have stopped all study drugs or all available data in the database snapshot for subjects still on treatment at the time of this analysis.

If the relevant baseline laboratory data are missing, then any abnormality of at least Grade 1 will be considered treatment emergent.

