18.11	CD4 Counts ( $\text{cells}/\text{mm}^3$ ) and Change from Baseline by Visit	Safety Analysis Set
18.12	CD4 Counts (%) and Change from Baseline by Visit	Safety Analysis Set
19.1	Treatment-Emergent Graded Laboratory Abnormalities	Safety Analysis Set
19.2	Treatment-Emergent Grade 3 or 4 Laboratory Abnormalities	Safety Analysis Set
20	Shift in Toxicity Grade for Total Bilirubin from Baseline to Maximal Post-baseline Grade by Atazanavir Status at Enrollment	Safety Analysis Set
21	Proportion of Subjects with HIV Virologic Rebound for Subjects Who Were on ARV Treatment at Enrollment	Safety Analysis Set
22.1	HCV Virologic Outcome for Subjects on ARV at Baseline	Full Analysis Set
22.2	HCV Virologic Outcome for Subjects Not on ARV at Baseline	Full Analysis Set
23.1	CD4 Counts ( $\text{cells}/\text{mm}^3$ ) and Change from Baseline by Visit for Subjects on ARV at Baseline	Safety Analysis Set
23.2	CD4 Counts ( $\text{cells}/\text{mm}^3$ ) and Change from Baseline by Visit for Subjects Not on ARV at Baseline	Safety Analysis Set
23.3	CD4 Counts (%) and Change from Baseline by Visit for Subjects on ARV at Baseline	Safety Analysis Set
23.4	CD4 Counts (%) and Change from Baseline by Visit for Subjects Not on ARV at Baseline	Safety Analysis Set

Figure Number	Title	Analysis Set
1.1	Median (Q1, Q3) ALT (U/L) by Visit	Safety Analysis Set
1.2	Median (Q1, Q3) AST (U/L) by Visit	Safety Analysis Set
1.3	Median (Q1, Q3) Total Bilirubin (mg/dL) by Visit	Safety Analysis Set
1.4	Median (Q1, Q3) Alkaline Phosphatase (U/L) by Visit	Safety Analysis Set
1.5	Median (Q1, Q3) WBC ( $\times 10^3/\mu\text{L}$ ) by Visit	Safety Analysis Set
1.6	Median (Q1, Q3) Neutrophils ( $\times 10^3/\mu\text{L}$ ) by Visit	Safety Analysis Set
1.7	Median (Q1, Q3) Lymphocytes ( $\times 10^3/\mu\text{L}$ ) by Visit	Safety Analysis Set
1.8	Median (Q1, Q3) Hemoglobin (g/dL) by Visit	Safety Analysis Set
1.9	Median (Q1, Q3) Platelets ( $\times 10^3/\mu\text{L}$ ) by Visit	Safety Analysis Set
1.10	Median (Q1, Q3) Reticulocytes ( $\times 10^3/\mu\text{L}$ ) by Visit	Safety Analysis Set
1.11	Median (Q1, Q3) CD4 Counts (cells/mm  ) by Visit	Safety Analysis Set
1.12	Median (Q1, Q3) CD4 Counts (%) by Visit	Safety Analysis Set
2.1	Median (Q1, Q3) CD4 Counts (cells/mm  ) by Visit by ARV at Baseline	Safety Analysis Set
2.2	Median (Q1, Q3) CD4 Counts (%) by Visit by ARV at Baseline	Safety Analysis Set
3.1	Forest Plot of SVR4 by Subgroup	Full Analysis Swet

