3.2	Forest Plot of SVR12 by Subgroup	Full Analysis Swet

Listing Number	Title	Analysis Set
1	Subject Disposition	Safety Analysis Set
2	Subject Demographics and Baseline Characteristics	Safety Analysis Set
3	Medical History	Safety Analysis Set
4	Study Drug Administration	Safety Analysis Set
5	Prior and Current HIV Medications	Safety Analysis Set
6	Subjects with HCV Virologic Failure	Full Analysis Set
7.1	HCV RNA (log10 IU/mL) and Change from Baseline for All Subjects in the FAS	Full Analysis Set
7.2	HCV RNA (log10 IU/mL) and Change from Baseline for All Subjects in the Safety Analysis Set but Not in FAS	Safety Analysis Set
8	All Adverse Events	Safety Analysis Set
9	Grade 3 or 4 Adverse Events	Safety Analysis Set

10	Adverse Events Leading to Permanent Discontinuation from Any of the Study Drugs	Safety Analysis Set
11	Adverse Events Leading to Permanent Discontinuation from SOF	Safety Analysis Set
12	Serious Adverse Events	Safety Analysis Set
13	Pregnancy	Safety Analysis Set
14	Deaths	Safety Analysis Set
15	Central Laboratory (Covance) Reference Ranges	Safety Analysis Set
16	Subjects with Treatment-Emergent Grade 3 or 4 Laboratory Abnormalities	Safety Analysis Set
17.1	Hematology: RBC, Reticulocyte Count, WBC, Lymphocytes, and Neutrophils	Safety Analysis Set
17.2	Hematology: Monocytes, Eosinophils, and Basophils	Safety Analysis Set
17.3	Hematology: Hemoglobin, Hematocrit, Platelets, and MCV	Safety Analysis Set
18	Coagulation and Thyroid Function: INR, PT, APTT	Safety Analysis Set
19.1	Chemistry: Albumin, Alkaline Phosphatase, ALT, AST, Total Bilirubin, and Direct Bilirubin	Safety Analysis Set
19.2	Chemistry: Serum Creatinine, Estimated GFR (Cockcroft-Gault)	Safety Analysis Set
19.3	Chemistry: Lipase, Potassium, Sodium, and Glucose	Safety Analysis Set
20	CD4 T-Lymphocyte Absolute Count and % and HIV RNA (copies/mL)	Safety Analysis Set
21	Height, Weight, BMI and Vital Signs	Safety Analysis Set
22.1	Subjects with HIV Virologic Rebound	Safety Analysis Set
22.2	HIV RNA, Change and Percent Change from Baseline by Visit for Subjects Not on ARV at Baseline	Safety Analysis Set

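### After baseline the SAP tabulates renal laboratory data only as a creatinine grade that starts above 1.50 mg/dL, so clearance falls of a third to a half can be left to a subject listing

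*Combined protocol and SAP*

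**What the plan says.** SAP 7.2.1 names the analytes to be summarized at baseline, at each later window and as change from baseline. Statistics are given "by treatment group for ALT, AST, total bilirubin, alkaline phosphatase, white blood cell (WBC) counts, neutrophils, lymphocytes, hemoglobin, platelets, reticulocytes, PT, and INR", with CD4 counts added at the end, and the list contains no renal measure. SAP Appendix 1 matches on this point: the by-visit laboratory tables run from ALT (18.1) to "CD4 Counts (%) and Change from Baseline by Visit" (18.12). Figures 1.1-1.12 cover the same analytes, and Tables 23.1-23.4 and Figures 2.1-2.2 are CD4 only.

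Renal data appear in three other places:

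- **Baseline.** SAP 5.1 summarizes Cockcroft-Gault eGFR among the baseline characteristics.
- **Grades.** Protocol Appendix 3 sets creatinine Grade 1 at "> 1.50 to 2.00 mg/dL". It has no criterion relative to baseline and no row for clearance. SAP 7.2.2.1 calls an abnormality treatment-emergent for "values that increase at least 1 toxicity grade from baseline at any time post-baseline", and these are counted in Table 19.1, "Treatment-Emergent Graded Laboratory Abnormalities".
- **Listing.** The title of Listing 19.2 begins "Chemistry: Serum Creatinine, Estimated GFR (Cockcroft-Gault". SAP 7.2.2.3 lists all laboratory values and flags those that are graded or outside the reference range.

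The listed antiretroviral regimens (Protocol 4.2 and 5.6.2) all combine emtricitabine/tenofovir with a further agent. Up to 10% of subjects may be untreated, and other combinations of the listed drugs can be allowed case by case.

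**The concern.** Safety and tolerability is a primary objective, and most subjects will take the study drugs on top of tenofovir. A reader would expect the tables to show whether renal function moved. Under this plan the tables answer only whether creatinine moved up a grade, the lowest step being 1.50 mg/dL. A subject with low baseline creatinine can lose much of the estimated clearance without crossing that line, and a small shift in everyone need not move anyone across it. The report could then state that no treatment-emergent creatinine abnormality occurred while some subjects had dropped below the trial's own entry limit of 60 mL/min. Only someone who worked through the listing would know.

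**Working it through.** **1. The plan's own limit.** Appendix 3 gives the creatinine limits in two units. The ratios are 133/1.50 = 88.7, 177/2.00 = 88.5, 265/3.00 = 88.3 and 530/6.00 = 88.3 µmol/L per mg/dL. The 1.50 mg/dL limit is therefore consistent and not a misprint.

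**2. Largest fall that stays Grade 0.** Protocol 6.4.5 gives CLcr = (140 − age) × weight / (72 × Scr), times 0.85 for women. With age, sex and weight fixed, clearance is inversely proportional to creatinine. A rise from baseline S0 to exactly 1.50 is still Grade 0, so the largest ungraded fall is 1 − S0/1.50, whatever the age, sex and weight.

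| Baseline creatinine (mg/dL) | Largest fall in CLcr still Grade 0 |
|---|---|
| 0.60 | 60% |
| 0.75 | 50% |
| 0.80 | 47% |
| 0.90 | 40% |
| 1.00 | 33% |

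**3. Illustrations.** Age, weight and creatinine are assumed, because the documents give no baseline distribution. Creatinine rises from 0.8 to 1.5 mg/dL.

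- Man, 50 years, 70 kg: 90 × 70 / (72 × 0.8) = 109.4, falling to 90 × 70 / (72 × 1.5) = 58.3 mL/min.
- Woman, 50 years, 60 kg: 90 × 60 × 0.85 / (72 × 0.8) = 79.7, falling to 90 × 60 × 0.85 / (72 × 1.5) = 42.5 mL/min.

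Both lose 47% and remain Grade 0. The man crosses 60 mL/min at a creatinine of 6300 / (72 × 60) = 1.46 mg/dL and the woman at 4590 / (72 × 60) = 1.06 mg/dL. Both values are ungraded.

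**4. Exact halving.** Halving clearance means doubling creatinine. The doubled value stays ungraded only if 2 × S0 ≤ 1.50, that is S0 ≤ 0.75 mg/dL. Above that it is graded and enters Table 19.1: 0.8 to 1.6 and 1.0 to 2.0 are Grade 1, and 1.2 to 2.4 is Grade 2. Over assumed ages of 30-60 years and weights of 55-90 kg, a creatinine of 0.75 corresponds to a baseline clearance of 69.3 to 155.8 mL/min in women and 81.5 to 183.3 in men. Halving from a baseline at or above the value for the subject's own age and weight is missed.

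**5. Group shift.** As an example, if a group's creatinine rose from 0.9 to 1.0 mg/dL, clearance would fall by 1 − 0.9/1.0 = 10%. No table would show it, because no mean or median of creatinine or eGFR is produced after baseline.

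**The case against.** The strongest reply is that the data are reported. Listing 19.2 gives creatinine and eGFR for every subject in the safety set. Under Protocol 8.5, laboratory changes that need intervention or lead to interruption or discontinuation of study drug must be recorded as adverse events, so they reach the adverse event tables. This SAP is also limited to key data for the 120-day response and the AASLD analysis (SAP 2.1), and Protocol 9.5.3 promises summaries of selected laboratory data only. All of this stands. No commitment is broken and no sections conflict.

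It does not close the gap. A listing gives neither a group change nor a count. Protocol 8.5 also says that laboratory abnormalities are usually not recorded as adverse events, so a silent fall would often remain in the listing. The analysis is meant to support a marketing application. The SAP already gives one antiretroviral-specific laboratory question its own table, the bilirubin shift by atazanavir status (Table 20). Tenofovir, the common backbone, has no renal counterpart.

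A reader might infer three stronger things that the documents do not support:

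- **That any halving of clearance escapes the tables.** This is true only from a baseline creatinine of 0.75 mg/dL or less. Above that, Table 19.1 counts it, though as a grade without the size of the fall.
- **That a renal effect could be neither seen nor excluded.** It could be worked out from Listing 19.2. The difference is between listed and tabulated.
- **That the interaction data signal renal harm.** The text with Protocol Table 1-1 makes an exception "of a slight increase in TDF Cmax (25%) that is not considered to be clinically significant". In the same rows tenofovir AUC (ratio 97.7%, 90% CI 91.1-105) and trough (98.6%, 91.3-106) were unchanged. Those data come from 16 healthy volunteers given single doses of GS-7977, so they do not settle 12 to 24 weeks of treatment. They are still not evidence of an interaction.

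**Conclusion.** The point holds as a reporting gap. After baseline, no creatinine or eGFR is summarized by visit, and the only tabulated renal laboratory result is a grade with a fixed limit of 1.50 mg/dL. Depending on baseline creatinine, a fall in clearance of 33% (from 1.0 mg/dL) to 50% (from 0.75), or more from lower baselines, can stay Grade 0 and appear only in Listing 19.2 unless it is reported as an adverse event. A modest group-wide shift appears in no table.

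The percentages follow from the protocol's formula at fixed weight and do not depend on the assumed subjects. The mL/min figures do. How many subjects could be affected is unknown, because the baseline creatinine distribution is not in the documents. The tenofovir background makes the gap worth closing, but up to 10% of subjects may take no antiretrovirals, and nothing here shows that harm occurs.

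**What to change.** 1. Add serum creatinine and Cockcroft-Gault eGFR, as value and change from baseline by visit, to SAP 7.2.1 and to the 18.x tables and matching figures.
2. Add the number and percent of subjects by maximum percent fall in eGFR from baseline (for example ≥ 25% and ≥ 50%), and with any post-baseline eGFR below 60 mL/min, the protocol's entry limit. Report both by treatment group and by tenofovir use at baseline. The count below 60 is not enough alone: a 50-year-old, 75-kg man whose creatinine doubles from 0.70 to 1.40 goes from 133.9 to 67.0 mL/min and would not be counted.
3. State which weight enters on-treatment eGFR, for example baseline or last available. During dosing, Protocol Appendix 2 schedules weight only at baseline and at end of treatment or early termination.

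Creatinine belongs to the chemistry panel drawn at every on-treatment visit (Protocol 6.4.1 and Appendix 2), and eGFR is already derived for Listing 19.2. The cost is a few extra descriptive tables and one sentence on weight, with no new data collection.

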### **7.2.2. Graded Laboratory Values**

The Gilead Grading Scale for Severity of Adverse Events and Laboratory Abnormalities will be used for assignment of toxicity grades to laboratory results for purposes of analysis as Grade 0, Grade 1 (mild), Grade 2 (moderate), Grade 3 (severe) or Grade 4 (potentially life threatening). Grade 0 includes all values that do not meet criteria for an abnormality of at least Grade 1.

Some laboratory tests have laboratory toxicity criteria for both increased and decreased levels; analyses for each direction (ie, increased, decreased) will be presented separately.

#### 7.2.2.1. Treatment-Emergent Laboratory Abnormalities

Treatment-emergent laboratory abnormalities are defined as values that increase at least 1 toxicity grade from baseline at any time post-baseline up to the last dose of any study drug plus 30 days (except CD4 which is through the end of the study) for subjects who have stopped all study drugs or all available data in the database snapshot for subjects still on treatment at the time of this analysis.

If the relevant baseline laboratory data are missing, then any abnormality of at least Grade 1 will be considered treatment emergent.

#### 7.2.2.2. Treatment-Emergent Marked Laboratory Abnormalities

Treatment-emergent marked laboratory abnormalities are defined as values that increase at least 3 grades from baseline at any time postbaseline up to last dose of any study drug plus 30 days (except CD4 which is through the end of the study) for subjects who have stopped all study drugs or all available data in the database snapshot for subjects still on treatment at the time of this analysis.

If the relevant baseline laboratory data are missing, then any Grade 3 or 4 on-treatment values will be considered treatment-emergent marked abnormalities.

#### 7.2.2.3. Summaries of Laboratory Abnormalities

The following summaries (number and percentage of subjects) of laboratory abnormalities using the Gilead Grading Scale will be provided (subjects categorized according to most severe post-baseline abnormality grade):

- TE graded laboratory abnormalities
- TE Grade 3 and 4 laboratory abnormalities

For all summaries of laboratory abnormalities, the denominator is the number of subjects with non-missing post-baseline values (up to 30 days after last dose of any study drug (except CD4 and HIV RNA data which will use data collected through the end of the study) for the laboratory parameter of interest.

A listing of TE Grade 3 or Grade 4 laboratory abnormalities will be provided. This listing will include the complete laboratory test profile for each laboratory test with the graded result throughout the study.

All laboratory values will be listed. Values falling outside of the relevant reference range and/or meeting Gilead Grading Scale will be flagged, as appropriate, in the data listings.

### **7.3. Body Weight, Height, BMI and Vital Signs**

A listing of height (at screening), body weight, BMI, SBP, DBP, pulse, and temperature will be provided.

### **7.4. Prior and Current HIV Medications**

A list of subjects' prior and current HIV medication data will be provided.

### **7.5. Other Safety Measures**

A data listing for cirrhosis determination will be provided for all subjects at screening.

A data listing will be provided for subjects who become pregnant during the study.

The shift in toxicity grade for total bilirubin from baseline to maximal grade at post-baseline will be summarized by Atazanavir (ATV) status at enrollment for each treatment group.

In addition, the following analysis will be conducted for subjects on ARV at baseline and for subjects not on ARV at baseline respectively:

- SVR12 endpoint analysis with the virologic outcome
- Summary of absolute value and change from baseline by visit for the following laboratory analytes: CD4 counts (absolute and %).

## **9. SOFTWARE**

SAS® Software Version 9.1. SAS Institute Inc., Cary, NC, USA.

nQuery Advisor(R) Version 7.0. Statistical Solutions, Cork, Ireland.

